### Assessment of Causality

- The investigator is obligated to assess the relationship between study intervention and each occurrence of each AE/SAE. The investigator will use clinical judgment to determine the relationship.
- The investigator will make a determination of the relationship of the AE to the study intervention using a 2-category system according to the following guidelines:
  - Not Related: The AE is definitely or most likely caused by the participant's clinical state or the study procedure/conditions.
  - Related: The AE follows a reasonable temporal sequence from administration of the drug, abates upon discontinuation of the drug, follows a known or hypothesized cause-effect relationship, and (if appropriate) reappears when the drug is reintroduced.
- A *reasonable possibility* of a relationship conveys that there are facts, evidence, and/or arguments to suggest a causal relationship, rather than a relationship cannot be ruled out.
- Alternative causes, such as underlying disease(s), concomitant therapy, and other risk factors, as well as the temporal relationship of the event to study intervention administration, will be considered and investigated.
- The investigator will also consult the IB and/or product information, for marketed products, in his/her assessment.
- For each AE/SAE, the investigator **must** document in the medical notes that he/she has reviewed the AE/SAE and has provided an assessment of causality.
- There may be situations in which an SAE has occurred, and the investigator has minimal information to include in the initial report to IRB/IEC. However, it is very important that the investigator always make an assessment of causality for every event before the initial transmission of the SAE data to IRB/IEC.
- The investigator may change his/her opinion of causality in light of follow-up information and send an SAE follow-up report with the updated causality assessment.
- The causality assessment is one of the criteria used when determining regulatory reporting requirements.

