### **2.3.1 Risk Assessment**

CNS-related effects (such as somnolence, sedation, and gait disturbance) have been identified as an important risk related to the mechanism of action of GNX. In placebo-controlled studies, the most common CNS effects were somnolence, dizziness, fatigue, sedation, and gait disturbance. Of the AEs present at frequency > 1% and 2 times the frequency of placebo in the aggregate AE data, all 12 AEs are related to CNS function. The most common CNS-related AEs that led to discontinuation reported in placebo-controlled studies were dizziness (GNX 1.1%; placebo 0.4%); somnolence (GNX 0.9%; placebo 0.4%); and fatigue (GNX 0.8%; placebo 0.1%). These CNS effects were typically non-serious, mild to moderate in severity, and did not lead to discontinuation of treatment. However, in Study 1042-SE-2001, 2 SAEs of sedation were reported and led to early discontinuation and revision of the reference safety information.

The safety assessments to be performed in this study include vital signs, physical, neurological, and developmental examinations, 12-lead electrocardiogram (ECG), clinical laboratory tests, AE assessments, and Columbia Suicide Severity Rating Scale (C-SSRS). These are standard evaluations to ensure participant safety in this clinical study.

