##### **8.4.4.1 Suspected Unexpected Serious Adverse Reaction**

A SUSAR is defined as an SAE that meets both the following criteria with respect to IP:

Suspected — is assessed as related to IP

Unexpected — compared to the IP-related AEs described in the IB, Reference Safety Information, the event meets any of the following criteria:

- The event has not been previously described.
- The event is now characterized as more severe.
- The event is now characterized more specifically (eg, an event of “interstitial nephritis” in a participant receiving an agent previously described as associated with “acute renal failure”).

In clinical trials involving ill participants, events considered related to the natural history of the disease under study or to lack of efficacy (that is, the event is considered more likely related to those factors than to other factors, including study drug) are not considered “unexpected”.

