#### **8.4.7 Disease-related Events and/or Disease-related Outcomes Not Qualifying as Adverse Events or Serious Adverse Events**

Symptoms of the disease under study should not be classified as AEs as long as they are within the normal day-to-day fluctuation or expected progression of the disease. This includes seizures typical for that participant unless the seizures are changed in character, frequency, or duration. Significant worsening of the symptoms should be recorded as an AE.

The following disease-related events are common in participants with epilepsy and can be serious/life-threatening:

- Seizures.
- SE.

- Falls/trauma/accidents.

As these events are typically associated with the disease under study, they will not be reported according to the standard process for expedited reporting of SAEs even though the event may meet the definition of an SAE. These events will be recorded within 5 business days of when they are reported to the site. These disease-related events will be monitored on a routine basis.

Note: However, if either of the following applies, then the event must be recorded and reported as an AE/SAE (instead of a disease-related event):

- The event is, in the investigator's opinion, of greater intensity, frequency, or duration than expected for the individual participant, or
- The investigator considers that there is a reasonable possibility that the event was related to study intervention.

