### 4.3. Statistical Methods for Primary Safety Analyses

#### 4.3.1. Adverse Events

Adverse events (AEs) are collected from the time of informed consent/assent through the defined follow-up period. AEs are coded using MedDRA dictionary, version 24.0 and are

categorized by system organ class (SOC) and preferred term (PT). A treatment-emergent AE (TEAE) is defined as an AE that starts or worsens on or after the first day of dosing with IP. Detailed by-patient listings of all AEs reported during the study will be provided and will include verbatim and coded terms for each AE.

For the safety Analysis Set, the following tabular summaries will be created:

- An overall summary of TEAEs will present the number and percentage of subjects with at least 1 reported TEAE, study drug related TEAE, serious TEAE, TEAE of Grade 3 or higher, study drug infusion interruption, and death
- TEAEs by system organ class and preferred term
- TEAEs by system organ class, preferred term, and maximum severity
- Study drug related TEAEs by system organ class and preferred term
- TEAEs by decreasing frequency of preferred term
- Moderate or severe TEAEs by system organ class and preferred term
- Moderate or severe study drug related TEAEs by system organ class and preferred term
- TEAEs that led to study drug infusion interruption by system organ class and preferred term
- Serious TEAEs by system organ class and preferred term
- Serious study drug related TEAEs by system organ class and preferred term

For incidence reporting, if a subject reported more than 1 AE that was coded to the same preferred term/system organ class, the subject will be counted only once for that specific preferred term/system organ class. For TEAEs presented by severity, the worst severity for each event during the clinical trial will be presented for each subject. If the severity is missing for a TEAE, then a severity of “Severe” will be assigned. The imputed values for severity assessment will be used for incidence summaries, while the actual values will be used in data listings.

For TEAEs presented by relationship to study drug, the closest relationship to study drug for each event during the clinical trial will be presented for each subject. If the relationship to investigational product is missing for a TEAE, a causality of “Related” will be assigned. The imputed values for relationship assessment will be used for incidence summaries, while the actual values will be presented in data listings.

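### The Related guideline in protocol 10.4.3 lists abatement on stopping the drug without a qualifier and Not Related is not its complement, so events with GNX continued, and fatal or irreversible events, fit neither category cleanly

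*Protocol*

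**What the plan says.** Protocol 10.4.3 (Assessment of Causality) tells the investigator to use clinical judgment and to classify each event "using a 2-category system according to the following guidelines". The two texts are:

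- The positive category: "Related: The AE follows a reasonable temporal sequence from administration of the drug, abates upon discontinuation of the drug, follows a known or hypothesized", with the rest of the list reading "abates upon discontinuation of the drug, follows a known or hypothesized cause-effect relationship, and (if appropriate) reappears when the drug is reintroduced".
- The negative category: "Not Related: The AE is definitely or most likely caused by the participant's clinical state or the study procedure/conditions".

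The next bullet explains a reasonable possibility as the presence of facts, evidence or arguments pointing to causation. It does not mention what happens when the drug is stopped. Causality must be given before an SAE is first transmitted, and it may be revised later.

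Three other places depend on the judgment or use a different test:

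- Protocol 8.4.7 moves a disease-related event into AE/SAE reporting when "The investigator considers that there is a reasonable possibility that the event was related to study intervention".
- Protocol 8.4.4.1 makes it the first of the two SUSAR criteria that the event "is assessed as related to IP".
- SAP 4.3.1 uses the field in four outputs: the related count in the overall summary, "Study drug related TEAEs by system organ class and preferred term", the moderate or severe related events, and the serious related events. A missing relationship is counted as related in the incidence summaries.

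**The concern.** A causality field with two options should divide all events between them. Here the positive option lists an observation that many events cannot supply, namely improvement after the drug is stopped. The negative option requires a positive attribution to something else. An investigator who thinks the drug may be responsible, and who has kept the participant on it, has no option that matches.

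The study has a single open-label arm, so no concurrent control separates drug effect from background. Investigator attribution therefore carries more weight than in a controlled trial. If about 75 sites resolve the gap in different ways, the related-event rates will partly reflect how each site read the paragraph. The same reading enters the site's contribution to the SUSAR decision.

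**Working it through.** The plan states no figure on this point to reproduce. The check is mainly textual, with one calculation for scale.

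**1. Structure of the two categories.** Related has four elements joined by a final 'and': timing, abatement on discontinuation, a known or hypothesized causal link, and reappearance. The bracketed qualifier is attached to reappearance alone. Not Related is met only when another cause is certain or most likely. An event with good timing and a plausible mechanism, but with no stop of the drug and no likely alternative cause, fully meets neither.

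**2. The protocol expects such events.**
- Section 6.2 lists maintaining or reducing the dose as approaches to AEs thought to be dose-related. Neither is a discontinuation.
- The participant dosing instructions (10.7) say side effects usually pass in 2 or 3 days, without mention of stopping.
- Section 8.4.6 says the action 'withdrawn' should not be chosen solely because of death, so a fatal event may show no discontinuation. It cannot abate in any case, and nor can an irreversible event.

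**3. Timing.** SAEs go to the safety vendor within 24 hours with causality already assessed. Stopping normally involves a 2-week taper. The clock for a fatal or life-threatening SUSAR is 7 days, and 7 is less than 14, so it can expire before a standard taper ends. Later revision of causality is allowed but may come after the deadline.

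**4. Two tests side by side.** Under 8.4.7 a seizure or fall becomes a reportable AE/SAE on a reasonable possibility. The same event is then classified under 10.4.3, whose category text does not use that term.

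**5. Scale.** Inputs are the GNX-group incidences in protocol 2.2.2.2 and the discontinuation rates for the same events in protocol 2.3.1, both described as coming from placebo-controlled studies. The formula is: share discontinuing = discontinuation % ÷ incidence %.

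| Event | Incidence | Discontinued for it | Share discontinuing | Remainder |
|---|---|---|---|---|
| Somnolence | 23.84% | 0.9% | 0.9/23.84 = 3.8% | 96.2% |
| Dizziness | 12.2% | 1.1% | 1.1/12.2 = 9.0% | 91.0% |
| Fatigue | 11.2% | 0.8% | 0.8/11.2 = 7.1% | 92.9% |

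Applied to the protocol's 169 participants, these rates give about 40 with somnolence (169 × 0.2384 = 40.3), of whom about 1.5 would stop for it (169 × 0.009). With the SAP's 150 the figures are 35.8 and 1.4. Section 2.3.1 says the same in words: "These CNS effects were typically non-serious, mild to moderate in severity, and did not lead to discontinuation of treatment".

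The remainder column is the share with no permanent discontinuation for that event. It is not a misclassification rate. Temporary interruptions would supply some further information on abatement, but the documents give no rate for them.

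**The case against.** The strongest reply is that the paragraph is not a rule. It calls itself guidelines, puts clinical judgment first, and explains reasonable possibility in the next bullet. It also demands causality before first SAE transmission, often before any abatement could be seen, which hardly suits an absolute requirement. Many investigators will attribute sensibly whatever the list says. All of this stands, and it limits the effect to inconsistency and some under-counting.

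A reader might infer more: that an event with the drug continued, or a fatal event, can never be called related, so that the related-event tables are emptied and the SUSAR route is blocked. The documents do not support that:

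- Such events do not default to Not Related, because that category has its own demanding condition.
- Even a strict reading leaves events that resolved after stopping. A blank causality field is counted as related in the SAP's incidence summaries.
- Protocol 8.4.1 sends every SAE to the sponsor's safety vendor within 24 hours whatever its relationship to the study. Section 8.4.4.1 does not restrict who makes the relatedness assessment, and 8.4.4 puts the duty to notify regulators on the sponsor.
- The primary endpoint of AE and SAE incidence and severity does not use this field. SAP 4.3.1 tabulates all TEAEs and all serious TEAEs regardless of relatedness.

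The reply does not remove the problem. Judgment exercised against guidance that points two ways will differ between sites. The missing-value rule acts only on blank fields, whereas 10.4.3 says an assessment must be documented for each event, and the rule changes tables, not expedited reporting.

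**Conclusion.** The wording is defective in three respects: abatement lacks the qualifier given to rechallenge, the two categories leave a gap between them, and the definition is not tied to the reasonable-possibility test used elsewhere in the protocol. The likely consequence is uneven attribution between sites and some under-counting in the four related-TEAE outputs and in the site assessment behind the SUSAR criterion.

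The size of that under-count cannot be estimated from the documents. The 3.8% to 9.0% range shows only that abatement after permanent discontinuation will seldom be available for the common CNS events. It assumes that the incidence and discontinuation figures share one pool and that similar proportions apply in this extension. The point merits correction because it touches safety attribution and costs little. It does not put the primary safety tables in doubt.

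**What to change.** In protocol 10.4.3:

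- Define Related as a reasonable possibility that the IP caused the event, using the explanation of that term already in the section.
- List timing, abatement after stopping, mechanism and rechallenge as supporting factors where applicable, none of them required.
- Define Not Related as no reasonable possibility, so that the two categories cover every event.
- Cross-refer 8.4.4.1 and 8.4.7 to this single definition.

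The minimum repair is to add 'if applicable' to the abatement element. That leaves the gap between the categories and the second test in place.

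The cost is one paragraph in an amendment and matching text in the eCRF completion guidelines. The two categories and the database field stay as they are. There are two downsides. The related-TEAE count will probably rise somewhat. The SAP cites CRFs dated 12 September 2024, well after protocol v4.0, so some events may already have been classified under the current wording. Those need either re-assessment or a note in the CSR on the change of definition, so that two definitions are not mixed unmarked in one table.

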### Follow-up of AEs and SAEs

- The investigator is obligated to perform or arrange for the conduct of supplemental measurements and/or evaluations as medically indicated or as requested by IRB/IEC to elucidate the nature and/or causality of the AE or SAE as fully as possible. This may include additional laboratory tests or investigations, histopathological examinations, or consultation with other health care professionals.
- If a participant dies during participation in the study or during a recognized follow-up period, the investigator will provide IRB/IEC with a copy of any postmortem findings including histopathology.
- New or updated information will be recorded in the originally submitted documents.
- The investigator will submit any updated SAE data to the sponsor within 24 hours of receipt of the information.

#### 10.4.4 Reporting of SAEs

##### SAE Reporting to IRB/IEC via Paper Data Collection Tool

- Facsimile or email transmission of the SAE paper data collection tool are the preferred methods to transmit this information to the Pharmacovigilance team/vendor.
- In rare circumstances and in the absence of available equipment, notification by telephone is acceptable with a copy of the SAE data collection tool sent by overnight mail or courier service.
- Initial notification via telephone does not replace the need for the investigator to complete and sign the SAE data collection tool within the designated reporting timeframes.
- Contacts for SAE reporting can be found in Section 10.2 and Study Operations Binder.

## **10.5 Appendix 5: Contraceptive and Barrier Guidance**

### **10.5.1 Female Contraception**

WOCBP must be using a medically acceptable form of birth control and have a negative quantitative serum  $\beta$ -HCG test collected at the initial visit. WOCBP must be advised to use medically acceptable birth control throughout the study period and for 30 days after the last dose of IP. These include intrauterine devices, hormonal contraceptives (eg, combined oral contraceptives, patch, vaginal ring, injectables, and implants), and surgical sterilization (such as oophorectomy or tubal ligation). When used consistently and correctly, "double-barrier" methods of contraception can be used as an effective alternative to highly effective contraception methods (see Section 10.5.3 for "double-barrier methods"). Contraceptive measures such as Plan BTM, sold for emergency use after unprotected sex, are not acceptable methods for routine use.

### **10.5.2 Male Contraception**

Male participants must agree to use highly effective contraceptive methods during the study and for 30 days after the last dose of IP. Highly effective methods of contraception include surgical sterilization (such as a vasectomy) and adequate "double-barrier" methods as described in Section 10.5.3.

Male participants should not donate sperm during the study and for 30 days after the last dose of IP.

### **10.5.3 Acceptable Barrier Methods of Contraception**

"Double-barrier" methods of contraception include male condom with diaphragm, or male condom with cervical cap.

## **10.6 Appendix 6: Country-specific Requirements**

All local laws and regulatory requirements will be complied with during this study.

## 10.7 Appendix 7: Dosing Instructions for Oral Suspension

### Ganaxolone 1042-TSC-3002 STUDY DOSING INSTRUCTIONS FOR ORAL SUSPENSION

Dose Maintenance / Dose Taper      *(Please circle phase)*

Participant ID and Initials: \_\_\_\_\_

Next Appointment: \_\_\_\_\_

Study Doctor (PI): \_\_\_\_\_

PI Telephone Number: \_\_\_\_\_

These are your study drug dosing instructions from now until your next visit.

Take the study drug three times each day with a meal or snack, plus approximately 4-8 oz of water.

Weight: \_\_\_\_\_ (in kg).

Start Date	DOSE (mL) 3 times/day

## **GANAXOLONE 1042-TSC-3002 STUDY DOSING INSTRUCTIONS FOR ORAL SUSPENSION**

Be sure that you read, understand, and follow these instructions carefully to ensure proper dosing of the oral suspension.

[figure not shown]
[figure not shown]
**Important:**

- Follow your study doctor's instructions for the dose of study drug to take or give. Study drug must be taken or given with food and used within 30 days of opening.
- Ask your study doctor if you are not sure how to prepare, take, or give the prescribed dose of study drug.
- Always use the oral syringe provided by your study doctor with study drug to make sure you measure the right amount of study drug.
- Do not consume grapefruit or grapefruit juice, Seville oranges, starfruits, or excessive quantities of alcohol during the study because it could interact with the study drug.
- Each dose should be separated by at least 4 hours and not more than 12 hours. An example schedule would be 1 dose at 8 am after breakfast, the next dose at 3 pm with a snack, and the third dose at 9 pm with a snack before bed.
- If you forget 1 dose and there is less than 4 hours before the next dose, skip that dose.
- If you miss 2 days of dosing or more, call the study doctor for instructions how to restart.
- Save all empty, partially used, and unused bottles of the study drug and return the bottles at your next visit.
- Some people may report feeling dizzy or tired, or experiencing other problems after taking the study drug. These side effects usually go away after 2 or 3 days. If you experience any side effects from the study drug that interfere with your daily activities or if you have any questions, please contact your study doctor to see if a dose adjustment is necessary.

**Materials provided by your study doctor:**

Child-resistant cap:	
Press-in bottle adapter:	
Bottle of study drug:	
Reusable oral syringe to take or give the dose of study drug:  Note: If you lose or damage an oral syringe, or cannot read the markings, use a new syringe. Contact your study doctor for extra syringes if you run out.	

**Prepare the bottle – to use study drug for the first time.**

1. Hold the bottle in your hand and shake it up and down well for 1 minute.
 
Always shake the bottle well for 1 minute and then let the bottle stand for 1 minute so that any foam built up during shaking can settle before measuring and giving each dose of study medication. This helps you measure the correct amount of medicine.
 
Note: This step is for each dose of the study drug.
	

2. Remove the child-resistant cap by pushing down while turning the cap to the left (counter-clockwise).
	

3. Puncture and peel off the induction seal from the bottle.
 
Note: This step is only for the first use of the bottle.
	

4. Push the press-in-bottle adapter firmly into the bottle. Firmly grasp the bottle in one hand and insert the press-in bottle adapter all the way in the bottle with other hand using constant pressure. Make sure the press-in bottle adaptor is fully inserted. If not fully inserted, small parts such as the bottle adaptor may become a choking hazard for children and pets.
 
Note: Do not remove the press-in bottle adapter from the bottle after it is inserted.
	

